8.9. Immunogenicity Assessments

Exploratory biomarker samples collected during the study will be used to perform any immunogenicity related assessments as deemed appropriate.

Treatment-emergent ADAs are defined in Section [9.4.6](#).

Samples with tirzepatide ADA detected will be titered and may then be evaluated for their ability to neutralize the activity of assigned treatment, tirzepatide-neutralizing antibodies. Samples with ADA detected will also be tested for cross-reactive binding to native GIP and GLP-1, and, if such is detected, may then be tested for neutralizing antibodies against native GIP and GLP-1.

8.10. Health Economics

Health economics and medical resource utilization parameters are not evaluated in this study.

9. Statistical Considerations

9.1. Statistical Hypotheses

The alternative hypothesis for the primary objective is the following:

- $H_{p,1}$: The pooled cohort of tirzepatide (5 mg, 10 mg, and 15 mg) QW is noninferior to insulin lispro (U100) TID, relative to the mean change in HbA1c from baseline to 52 weeks.

The alternative hypotheses for the key secondary objectives controlled for type 1 error rate are the following:

- $H_{p,2}$: The pooled cohort of tirzepatide (5 mg, 10 mg, and 15 mg) QW is superior to insulin lispro (U100) TID, relative to mean change in HbA1c from baseline to 52 weeks.
- $H_{p,3}$: The pooled cohort of tirzepatide (5 mg, 10 mg, and 15 mg) QW is superior to insulin lispro (U100) TID, relative to mean change in body weight from baseline to 52 weeks.
- $H_{p,4}$: The pooled cohort of tirzepatide (5 mg, 10 mg, and 15 mg) QW is superior to insulin lispro (U100) TID, relative to proportion of participants achieving target value of HbA1c < 7% at 52 weeks.
- $H_{5,1}, H_{10,1}, H_{15,1}$: Each of tirzepatide (5 mg, 10 mg, and 15 mg) QW is noninferior to insulin lispro (U100) TID, relative to mean change in HbA1c from baseline to 52 weeks.
- $H_{5,2}, H_{10,2}, H_{15,2}$: Each of tirzepatide (5 mg, 10 mg, and 15 mg) QW is superior to insulin lispro (U100) TID, relative to mean change in HbA1c from baseline to 52 weeks.
- $H_{5,3}, H_{10,3}, H_{15,3}$: Each of tirzepatide (5 mg, 10 mg, and 15 mg) QW is superior to insulin lispro (U100) TID, relative to mean change in body weight from baseline to 52 weeks.

The details of family-wise type I error rate control strategy and methods for the aforementioned hypotheses will be provided in the SAP.

9.2. Sample Size Determination

Participants will be randomized in a 1:1:1:3 ratio to tirzepatide (5 mg, 10 mg, 15 mg) QW or insulin lispro (U100) TID. The randomization ratio is determined to optimize safety assessment between the pooled cohort of tirzepatide (5 mg, 10 mg, and 15 mg) QW and insulin lispro (U100).

Although the primary objective of the trial is to demonstrate that the pooled cohort of tirzepatide (5 mg, 10 mg, and 15 mg) QW is noninferior to insulin lispro (U100) TID, relative to the primary endpoint (mean change in HbA1c from baseline to 52 weeks) with a 0.3% noninferiority margin, sample size selection is guided by establishing noninferiority of each tirzepatide dose, tested against insulin lispro (U100), relative to the primary endpoint (mean change in HbA1c from baseline to 52 weeks).

The sample size determination assumes that evaluation of noninferiority of individual tirzepatide dose to insulin lispro (U100) will be conducted, each at a one-sided significance of 0.025, using a two-sample t-test. Additionally, a 0% difference in mean change in HbA1c from baseline to 52 weeks for each tirzepatide arm compared with insulin lispro (U100); a common SD of 1.3% (accounting for increase in SD due to the inclusion of data on rescue medications and after premature treatment discontinuation and imputation of missing data) and a noninferiority margin of 0.3% are assumed for statistical power calculations. On the basis of these assumptions, randomizing 1182 participants in a 1:1:1:3 ratio to tirzepatide 5 mg (197 participants), tirzepatide 10 mg (197 participants), tirzepatide 15 mg (197 participants) and insulin lispro (U100) (591 participants) provides 80% power to demonstrate noninferiority of each tirzepatide dose to insulin lispro (U100).

Furthermore, this sample size will ensure 97% power to establish noninferiority of the pooled cohort of tirzepatide (5 mg, 10 mg, and 15 mg) compared to insulin lispro (U100), using a 2-sample t-test at 1-sided significance level of 0.025, provided a 0.0% difference in mean change in HbA1c from baseline to 52 weeks for the pooled cohort of tirzepatide doses compared with insulin lispro (U100), a common SD of 1.3% and noninferiority margin of 0.3%.

9.3. Populations for Analyses

Table 15. Populations for Analyses

Population	Description
Screened participants	All participants who sign informed consent.
Randomized participants	All participants who are randomly assigned to a treatment arm.
mITT population	All randomly assigned participants who are exposed to at least 1 dose of study intervention, that is, tirzepatide or insulin lispro (U100). In the event of a treatment error, participants will be analyzed according to the treatment they were randomized.
EAS	Data obtained during Study Period II from the mITT population, excluding data after initiating rescue antihyperglycemic medication or stopping study intervention.
FAS	Data obtained during Study Period II from the mITT population, regardless of adherence to study intervention or initiation of rescue antihyperglycemic medication.
SS	Data obtained during Study Periods II or III from the mITT population, regardless of adherence to study intervention or initiation of rescue antihyperglycemic medication.

Abbreviations: EAS = efficacy analysis set; FAS = full analysis set; mITT = modified intention-to-treat; SS = safety analysis set.

9.4. Statistical Analyses

9.4.1. General Considerations

Statistical analysis of this study will be the responsibility of Lilly or its designee.

Any change to the data analysis methods described in the protocol will require an amendment ONLY, if it changes a principal feature of the protocol. Any other change to the data analysis methods described in the protocol, and the justification for making the change, will be described in the SAP or Clinical Study Report. Additional exploratory analyses of the data will be conducted, as deemed appropriate.

Unless otherwise noted, all tests of treatment effects will be conducted at a 2-sided alpha level of 0.05, and the CI will be calculated at 95%, 2-sided. In statistical summaries and analyses, participants will be analyzed as randomized.

There will be 2 estimands of interest in comparing efficacy of tirzepatide doses with insulin lispro (U100). The first estimand, the “efficacy” estimand, represents efficacy prior to discontinuation of study intervention without the confounding effects of antihyperglycemic rescue therapy. The second estimand, the “treatment-regimen” estimand, represents the efficacy irrespective of adherence to study intervention or initiation of rescue antidiabetic drugs.

The primary efficacy assessment, guided by the “efficacy” estimand, will be conducted using the EAS. The primary efficacy assessment, guided by the “treatment-regimen” estimand, will be conducted using the FAS. As they are intended for different purposes, no multiplicity adjustments will be made for conducting the 2 primary efficacy assessments.

Unless specified otherwise, safety assessments will be guided by an estimand comparing safety of tirzepatide (5 mg, 10 mg, and 15 mg) with insulin lispro (U100), irrespective of adherence to study intervention or initiation of antihyperglycemic rescue therapy. Thus, the safety analysis will be conducted using the SS. Selected safety analysis (for example, hypoglycemia) may be conducted excluding data after introducing another antihyperglycemic therapy.

Summary statistics for continuous measures will include sample size, mean, SD, median, minimum, and maximum. The analysis model to make comparisons among treatment arms relative to continuous measurements assessed over time will be an MMRM, with terms of treatment, visit and treatment-by-visit interaction, country, metformin use (Yes or No), and baseline measurement as a covariate. An unstructured covariance matrix will model the relationship of within-participant errors.

The Kaplan-Meier method will be used for estimation of cumulative event-free survival rates over time, and cox proportional hazards regression analysis will be used to compare hazard rates among treatments.

Summary statistics for categorical measures, including categorized continuous measures, will include sample size, frequency, and percentages. Fisher's exact test will be used to examine the treatment difference in categorical outcomes. Logistic regression may be used to examine the treatment difference in binary efficacy outcomes. Summary statistics for discrete count measures will include sample size, mean, SD, median, minimum, and maximum. The negative binomial regression model will be used for the treatment comparison of discrete count measures.

Other statistical methods may be used, as appropriate, and details will be documented in the SAP.

9.4.2. Treatment Arm Comparability

9.4.2.1. Participant Disposition

Frequency counts and percentages of all participants screened, randomized, and receiving at least 1 dose of study intervention (tirzepatide or insulin lispro [U100]), will be presented by treatment arm. Of the participants in the mITT population, frequency, counts and percentages of participants completing the study, prematurely discontinuing the study, including the reason for premature discontinuation, will be presented by treatment arm. A Kaplan-Meier analysis of time from randomization to premature discontinuation from study by treatment arm will be provided.

9.4.2.2. Participant Characteristics

Demographics, medical history, and concomitant illness will be summarized by treatment arm using the mITT population.

9.4.2.3. Concomitant Therapy

Concomitant medications, including previous therapy for diabetes, will be summarized by anatomical therapeutic chemical classification and treatment arm using the mITT population. In particular, the incidence of rescue therapy for severe, persistent hyperglycemia will be analyzed as an exploratory safety endpoint. Dose modifications of oral antihyperglycemic therapy will also be compared between treatment arms.

9.4.2.4. Treatment Compliance

Of the participants in the mITT population, frequency counts and percentages of participants prematurely discontinuing study interventions, including the reason for premature discontinuation, will be presented by treatment arm. A Kaplan-Meier analysis of time from randomization to premature study intervention discontinuation by treatment arm will be provided.

Treatment compliance is defined as taking at least 75% of required injections of study intervention. Frequency counts and percentages of participants compliant to study intervention will be summarized by treatment arm using the mITT population.

9.4.3. Efficacy Analyses

9.4.3.1. Primary Analyses

As indicated in Section 9.4.1., there will be 2 primary efficacy analyses conducted to establish noninferiority of the pooled cohort of tirzepatide at 5 mg, 10 mg, and 15 mg to insulin lispro (U100) relative to mean change in HbA1c from baseline to the 52-week visit.

The primary efficacy analysis regarding the “treatment-regimen” estimand, defined in Section 9.4.1., will analyze change in HbA1c values obtained at the 52-week visit using an ANCOVA with terms of treatment, country, metformin use (Yes or No), and baseline HbA1c as a covariate. Missing change in HbA1c from baseline values at the 52-week visit will be imputed based on observed changes in HbA1c from baseline values at the visit from participants in the same treatment arm who had their efficacy assessed after early discontinuation of study intervention and/or initiation of rescue antihyperglycemic medication. Analysis will be conducted with multiple imputations, and statistical inference over multiple imputations will be guided by the method proposed by Rubin.³³

The ANCOVA analysis will report least square means and standard error values for the pooled cohort of tirzepatide doses and insulin lispro (U100) as well as the difference in mean change in HbA1c from baseline to the 52-week visit. Two-sided 95% CI for the difference in mean change in HbA1c from baseline to 52-week visit between the pooled cohort of 5 mg, 10 mg, and 15 mg tirzepatide and insulin lispro (U100) will be constructed. The mean change in HbA1c from baseline to the 52-week visit will be calculated as subtracting the baseline HbA1c from the 52-week HbA1c. The difference between the pooled tirzepatide cohort and insulin lispro (U100) will be calculated as subtracting the mean change in HbA1c for insulin lispro (U100) from the mean change of HbA1c for the pooled tirzepatide cohort. If the upper limit of the CI is below 0.3%, the pooled cohort of 5 mg, 10 mg, and 15 mg QW tirzepatide will be declared noninferior to insulin lispro (U100).

The primary efficacy analysis regarding the “efficacy” estimand, defined in Section 9.4.1., will be conducted using the EAS. The primary analysis model for HbA1c measurements over time will be an MMRM. The response variable of MMRM will be change in HbA1c from baseline values obtained at each scheduled postbaseline visit. The independent variables of the MMRM model are treatment (pooled cohort of 5 mg, 10 mg, and 15 mg QW tirzepatide, and insulin lispro [U100]), visit, and treatment-by-visit interaction, country, metformin use (Yes or No), and baseline HbA1c as a covariate. An unstructured covariance structure will model the relationship of within-participant errors. If the analysis fails to converge, the following variance-covariance

matrix will be used, in order, until convergence is achieved: heterogeneous compound symmetry, compound symmetry, and first-order autoregressive. The Kenward-Roger approximation will be used to estimate denominator degrees of freedom.

The MMRM analysis will report least square means and standard error values for the pooled cohort of tirzepatide doses and insulin lispro (U100) as well as the difference in mean change in HbA1c from baseline to the 52-week visit. With the aid of the MMRM analysis, 2-sided 95% CI for the difference in mean change in HbA1c from baseline to the 52-week visit between the pooled cohort of 5 mg, 10 mg, and 15 mg tirzepatide, and insulin lispro (U100) will be constructed. The mean change in HbA1c from baseline to 52-week visit will be calculated as subtracting the baseline HbA1c from the 52-week HbA1c. The difference between the pooled tirzepatide cohort and insulin lispro (U100) will be calculated as subtracting the mean change in HbA1c for insulin lispro (U100) from the mean change of HbA1c for the pooled tirzepatide cohort. If the upper limit of the CI is below 0.3%, the pooled tirzepatide cohort will be declared noninferior to insulin lispro (U100).

9.4.3.2. Secondary Analyses

The secondary study objectives subject to type 1 error rate control are as follows:

- superiority of pooled tirzepatide (5 mg, 10 mg, and 15 mg) QW to insulin lispro (U100) TID, relative to mean change in HbA1c from baseline to 52 weeks
- superiority of pooled tirzepatide (5 mg, 10 mg, and 15 mg) QW to insulin lispro (U100) TID, relative to mean change in body weight from baseline to 52 weeks
- superiority of pooled tirzepatide (5 mg, 10 mg, and 15 mg) QW to insulin lispro (U100) TID, relative to proportion of participants achieving target value of HbA1c < 7% at 52 weeks
- noninferiority of each tirzepatide dose to insulin lispro (U100), relative to mean change in HbA1c from baseline to 52 weeks
- superiority of each tirzepatide dose to insulin lispro (U100), relative to mean change in HbA1c from baseline to 52 weeks
- superiority of each tirzepatide dose to insulin lispro (U100), relative to mean change in body weight from baseline to 52 weeks

The type I error-controlled strategy for the primary and secondary endpoints will be described in the SAP. All type I error-controlled secondary efficacy analyses will be conducted relative to both estimands, the “efficacy” estimand and the “treatment-regimen” estimand.

Analysis of change from baseline in body weight at the 52-week visit will be conducted in a manner similar to the primary efficacy analyses with change in body weight from baseline as the response variable, baseline body weight as a covariate, and HbA1c ($\leq 8.5\%$ or $>8.5\%$ [69 mmol/mol]) as a stratification factor.

Comparisons among treatments relative to the proportion of participants achieving the HbA1c target value of <7.0% (53 mmol/mol) at the 52-week visit will be conducted using a logistic regression analysis with terms of treatment, country, metformin use (Yes or No), and baseline HbA1c as a covariate. In the analysis of participants achieving the HbA1c target value relative to the “efficacy” estimand, subjects with missing values at the 52-week visit will be excluded. In the analysis of participants achieving the HbA1c target value relative to the “treatment-regimen” estimand, missing values at the 52-week visit will be imputed based on observed data at respective visits from participants in the same treatment arm who had their efficacy assessed after early discontinuation of study intervention and/or initiation of rescue medication. The analysis will be conducted with multiple imputations and statistical inference over multiple imputations will be guided by the method proposed by Rubin.³³

Analyses of actual and change from baseline in PRO scores will be conducted using linear models with baseline PRO scores, treatment, and other factors that may be considered relevant. These variables will be specified in the SAP.

9.4.3.3. Tertiary/Exploratory Analyses

All exploratory efficacy analyses will be guided by the “efficacy” estimand without imputation of missing data and will be conducted using the EAS. Details will be provided in the SAP.

9.4.4. Safety Analyses

Unless specified otherwise, safety assessments will be guided by an estimand comparing safety of the pooled cohort of tirzepatide doses with insulin lispro (U100) irrespective of adherence to study intervention(s) or initiation of rescue therapy. Thus, safety analyses will be conducted using the SS. Selected safety analyses may be conducted excluding data after the introduction of another antihyperglycemic therapy.

Adverse events will be coded from the actual term using MedDRA and reported with preferred terms and system organ class. Selected notable AEs of interest may be reported using high-level terms or Standardized MedDRA Queries. Summary statistics will be provided for incidence of TEAEs, SAEs, study discontinuation due to AEs, study intervention(s) discontinuation due to AEs, deaths, and other CV endpoints. Counts and proportions of subjects experiencing AEs will be reported for each treatment arm, and Fisher’s exact test will be used to compare the treatment arms.

9.4.4.1. Hypoglycemic Events

Incidence of documented symptomatic hypoglycemia events and severe hypoglycemia will be compared between the pooled cohort of tirzepatide doses and insulin lispro (U100) using negative binomial regression analysis. Selected safety analyses may be conducted excluding data after introduction of another antihyperglycemic therapy, for example, rescue therapy.

9.4.4.2. Gastrointestinal Events

Summaries and analyses for incidence and severity of nausea, vomiting, and diarrhea will be provided by each treatment.

9.4.4.3. Adjudicated Cardiovascular Events

Listings of deaths, myocardial infarctions, strokes, and hospitalization for unstable angina confirmed by an independent CEC will be provided. The dates of randomization, event, first dose and last dose of study intervention, and time from randomization to the event will be listed.

9.4.4.4. Central Laboratory Measures and Vital Signs

Values and change from baseline to postbaseline values of central laboratory measures and vital signs will be summarized at each scheduled visit. The analysis model to make comparisons among treatment arms, relative to continuous change from baseline values assessed over time will be an MMRM similar to the primary efficacy analysis and with baseline measurement as a covariate. An unstructured covariance structure will model the relationship of within-participant errors.

The percentages of participants with TE abnormal, high, or low laboratory measures at any time will be summarized and compared between treatment arms by using Fisher's exact test. A TE abnormal value is defined as a change from normal value at baseline to a value greater than the high limit at any time during Periods II and III. A TE low result is defined as a change from a value greater than or equal to the low limit at baseline to a value less than the low limit at any time during Periods II and III. High and low laboratory limits will be determined by the central laboratory reference ranges.

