6.13. Safety Analyses

Unless specified otherwise, safety assessments will be based on the Safety analysis Set (see [Table GPHD.6.1](#)). All events that occur between the date of first dose of study drug (ie, tirzepatide or insulin lispro [U100]) to the date of the patient's safety follow-up visit or the patient's end of study participation will be included, regardless of the adherence to study drug or initiation of rescue therapy. For assessing the benefit- risk profile through 52 weeks, selected safety analyses will be conducted by utilizing safety data from first dose through the date of the 52-week visit. Some safety analyses may be conducted after excluding data after initiation of new antihyperglycemic therapy. Additional safety analyses may be conducted using the LAS data set.

Unless specified otherwise, statistical assessment of homogeneity of the distribution of categorical safety responses among treatment arms (pooled cohort of tirzepatide doses and insulin lispro) will be conducted using Fisher exact test.

Unless specified otherwise, differences among treatment mean changes from baseline in continuous safety parameters at all scheduled visits will be assessed via an MMRM using REML. The model will include treatment, visit, treatment-by-visit interaction, country/pooled country, baseline HbA1c ($\leq 8.5\%$, $>8.5\% [\leq 69, >69 \text{ mmol/mol}]$), and baseline metformin use (Yes/No) as fixed effects, and baseline value of the safety parameter as a covariate. To model the covariance structure within patients, the unstructured covariance matrix will be used. If this model fails to converge, the covariance structures specified in Section [6.12.1.1](#) will be tested in order.

Unless specified otherwise, statistical summaries and analyses of safety assessments will be displayed in the following treatment order: individual tirzepatide doses (5 mg, 10 mg, 15 mg), pooled cohort of tirzepatide doses and insulin lispro (U100).

For selected safety parameters, time-to-first-event analysis via the Cox proportional hazards model may be conducted. For patients without an event, the “time-to-event” will be time (in days) from first dose to end of study participation. For patients experiencing the event, “time-to-first-event” will be the time (in days) from first dose to first occurrence of the event.

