6.13.2.3.1. Pancreatic Enzyme Assessment

Observed pancreatic enzyme data (p-amylase and lipase) will be summarized by treatment and nominal visit. The number and proportion of patients with maximum postbaseline pancreatic enzyme values exceeding the following thresholds will be provided by baseline pancreatic enzyme value (\leq upper limit of normal [ULN], $>$ ULN), and treatment: (>1 to ≤ 3) \times ULN, (>3 to ≤ 5) \times ULN, (>5 to ≤ 10) \times ULN, $>10 \times$ ULN.

An MMRM analysis will be used to analyze each pancreatic enzyme with a log transformed (postbaseline measure/baseline measure) response variable and country/pooled country, baseline metformin use (Yes/No), baseline HbA1c category ($\leq 8.5\%$, $>8.5\%$ [≤ 69 , > 69 mmol/mol]), treatment, visit, and treatment-by-visit interaction as fixed effects.

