Observed and change from baseline values for selected measurements for each visit will be displayed graphically for patients who have both a baseline and a postbaseline planned measurement. Unplanned measurements will be excluded from graphs.

Shift tables will be produced for selected measurements. A shift table will include unplanned measurements. The shift table will include the number and percentage of patients within each baseline category (low, normal, high, or missing) versus each postbaseline category (low, normal, high, or missing) by treatment. The proportion of patients shifted will be compared between treatments.

For qualitative laboratory analytes, the number and percentage of patients with normal and abnormal values will be summarized by treatment.

A listing of abnormal findings will be created for laboratory analyte measurements, including qualitative measures. The listing will include patient ID, treatment group, laboratory collection date, study day, analyte name, and analyte finding.

6.14. *Health Outcomes*

The patient-reported outcome questionnaires will be completed by the patients at baseline and at 52 weeks (or early termination visit prior to 52 weeks). These include use of the mITT

population on the FAS, and use of a 2-sided alpha level of 0.05 and a 2-sided 95% CI for pairwise comparisons.

No multiplicity adjustment will be made in the evaluation of health outcome measures. Item-level missingness is dealt with as per the instrument developer's instruction.

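### Laboratory safety comparisons: treatment-emergent high is left undefined in the protocol, the SAP's shift comparison has no direction, and UACR is analysed as raw change by default

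*Protocol*

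**What the plan says.** **Protocol 9.4.4.4.** Three TE categories (abnormal, high, low) are to be compared between arms by Fisher's exact test. Two rules follow. The first reads: "A TE abnormal value is defined as a change from normal value at baseline to a value greater than the high limit". The second defines TE low as at or above the low limit at baseline and below it later. There is no rule for TE high. For continuous measures: "The analysis model to make comparisons among treatment arms, relative to continuous change from baseline values assessed over time will be an MMRM". No transformation is stated.

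**SAP 6.13.5.** Shift tables with categories low, normal, high and missing are produced for selected measurements. Then: "The proportion of patients shifted will be compared between treatments". The section does not say which shifts count or how the missing category is treated, and it contains no TE high or TE low rule.

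**SAP 6.13.** The default rule is: "differences among treatment mean changes from baseline in continuous safety parameters at all scheduled visits will be assessed via an MMRM using REML". Each measure's own baseline enters as a covariate.

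**SAP 6.13.2.3.1.** An exception is made here: "An MMRM analysis will be used to analyze each pancreatic enzyme with a log transformed (postbaseline measure/baseline measure) response variable".

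**SAP 6.13.2.14.** Renal laboratory measures are referred to 6.13.5. UACR also gets a max-to-max table in the bands below 30, 30 to 300 and above 300 mg/g. The sentence allowing log transformation in SAP 6.12.4 applies to secondary and exploratory efficacy measures.

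**The concern.** **Definitions.** A programmer working from the protocol has three categories and two rules. The rule under the abnormal label excludes every low result. The two rules are also asymmetric: a participant who goes from high to low counts as TE low, but one who goes from low to high is counted nowhere.

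**Direction.** Under the literal SAP wording, a participant whose result normalizes adds to the shifted count exactly as one whose result becomes abnormal. If one arm improves more than the other, the two effects offset. Protocol 2.1 anticipates a difference in weight change between the regimens, so unequal improvement in some analytes is plausible.

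**Scale.** UACR is right-skewed. On raw change, a few participants with very high values set the residual variance, and a proportional change in the rest is hard to see. The SAP specifies a log ratio for pancreatic enzymes but not for UACR.

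**Working it through.** **1. Arm sizes and the plan's own figure.** Protocol 9.2: "Participants will be randomized in a 1:1:1:3 ratio to tirzepatide (5 mg, 10 mg, 15 mg) QW or insulin lispro (U100) TID", which gives 197/197/197/591, so pooled tirzepatide v lispro is 591 v 591. The stated power uses "a common SD of 1.3" percentage points, a margin of 0.3, a true difference of 0, "each at a one-sided significance of 0.025, using a two-sample t-test". Power = Φ(0.3 / (1.3 × √(1/n₁ + 1/n₂)) − 1.96):

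- per dose, 197 v 591: Φ(2.805 − 1.96) = 80.1% (stated 80%)
- pooled, 591 v 591: Φ(3.967 − 1.96) = 97.8% (stated 97%)

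These figures reproduce and are not disputed. They serve only to fix the arm sizes below. Laboratory tests use two-sided 0.05 (protocol 9.4.1).

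**2. Undirected v directed comparison.** The documents give no laboratory shift rates, so all rates here are assumptions. Shifted = worsened + improved. Fisher's exact test, 591 per arm, arms labelled A and B:

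| Worsen A v B | Improve A v B | Shifted A v B | p, shifted | Worsened A v B | p, worsened |
|---|---|---|---|---|---|
| 8% v 4% | 4% v 8% | 71 v 71 | 1.00 | 47 v 24 | 0.007 |
| 6% v 3% | 3% v 6% | 53 v 53 | 1.00 | 35 v 18 | 0.024 |
| 10% v 5% | 5% v 10% | 89 v 89 | 1.00 | 59 v 30 | 0.002 |
| 8% v 4% | 4% v 12% | 71 v 95 | 0.054 | 47 v 24 | 0.007 |
| 8% v 4% | 2% v 2% | 59 v 36 | 0.018 | 47 v 24 | 0.007 |

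In rows 1 to 3 a doubling of worsening disappears. In row 4 the arm with more worsening has fewer shifted participants, although not significantly at 0.05. In row 5, with equal improvement, the undirected test still finds the difference.

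An ALT-type example, with 20% high at baseline. Tirzepatide: 50% of those normalize and 4% of the rest become high. Lispro: 25% and 8%.

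- Shifted: 0.2 × 0.50 + 0.8 × 0.04 = 13.2% v 0.2 × 0.25 + 0.8 × 0.08 = 11.4%, i.e. 78 v 67 of 591, p = 0.375.
- TE high among those at risk (0.8 × 591 = 473): 19 v 38, p = 0.013.

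Here the undirected test misses a benefit. It does not produce a significant reversal.

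**3. UACR, raw change v log ratio.** All inputs are assumed: bivariate lognormal with median 20 mg/g, 532 per side (about 0.9 × 591), correlation 0.70 or 0.85, true ratio 0.80. A single-visit ANCOVA with its own baseline as covariate stands in for the MMRM; 1500 simulated trials per setting.

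| Log SD | Power raw (corr 0.70 / 0.85) | Power log (corr 0.70 / 0.85) |
|---|---|---|
| 1.0 | 94% / 99% | 99.9% / 100% |
| 1.3 | 59% / 77% | 97% / 99.9% |
| 1.6 | 30% / 43% | 89% / 99% |

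Type I error is near 5% on both scales.

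For a rise (591 per arm, correlation 0.75, median 15 mg/g, 2000 trials per setting), power at log SD 1.0, 1.3 and 1.6 is:

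- 20% rise: 88%, 52%, 25% raw v 99.7%, 95%, 84% log
- 10% rise: 39%, 19%, 10% raw v 70%, 49%, 33% log

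A significant result in the wrong direction occurs in at most 0.4% of trials.

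**The case against.** **The protocol rule already catches normal-to-high.** True. In the ALT-type example, with nobody low at baseline, it gives the directed result. The quoted sentence is most likely the TE high rule with the wrong label. What remains is the low-to-high change and a named category with no rule; nothing in the documents says how many participants this would affect.

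**The SAP does not withdraw the protocol's rules.** This also stands. A reader might infer that the SAP has replaced the directed categories with the undirected comparison, but the documents do not say so. SAP 6.2 says that changes to protocol methods will be described and justified in the SAP or CSR, the SAP's list of major changes contains no such removal, and SAP 6.13 keeps Fisher's exact test as the default for categorical safety responses. The accurate statement is that the SAP is silent on TE high and low, and that its own comparison has no stated direction.

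**Direction stays visible elsewhere.** SAP 6.13.2.12.3 and 6.13.2.14 give ordered shift tables for ALT, AST, bilirubin, ALP, eGFR and UACR. SAP 6.13.2.3.1 and 6.13.2.4.1 band pancreatic enzymes and calcitonin by baseline, and the general shift table shows every cell. A clear signal in these analytes would be seen descriptively. No directed between-arm test is specified for these tables, however, and they do not cover hematology or the remaining chemistry.

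**The raw-scale UACR test is valid.** It is. The issue is efficiency, and raw change applies to UACR by default rather than by an explicit choice.

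**Conclusion.** The point holds as a gap in specification. One of the protocol's three tested categories has no definition, and the SAP's only general categorical laboratory comparison has no direction. Taken literally, that comparison can hide a doubling of worsening (p = 1.00 v 0.007), but only when improvement differs between arms enough to offset it. The rates are assumed.

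For UACR the consequence is lost power: roughly 30% to 77% raw v 89% to 99.9% log for a 20% reduction at log SD 1.3 to 1.6. At log SD 1.0 the loss is small for that effect, though larger for a 10% rise (39% v 70%). The SDs, correlations, median and effect sizes are all assumptions.

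Three stronger readings are not supported:

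- That low results are lost under the protocol: TE low has its own correct rule.
- That the raw scale would reverse a UACR signal: significant wrong-sign results are at most 0.4%.
- That ALT and AST need a log scale: no calculation here shows it.

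No primary or key secondary efficacy conclusion is affected.

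**What to change.** 1. **Protocol 9.4.4.4.** Define TE high as at or below the high limit at baseline and above it at any later time in Periods II and III. Keep the TE low rule. Either define TE abnormal separately (for example, for qualitative tests) or remove it. If the protocol is not to be amended, SAP 6.2 allows the SAP to carry a change that is not a principal feature.
2. **SAP 6.13.5.** Replace the undirected comparison with two Fisher's exact tests, TE high and TE low, each among participants at risk at baseline and excluding those with a missing baseline or post-baseline category. Keep the shift tables as descriptive output.
3. **SAP 6.13.2.14 or 6.13.5.** Analyse UACR by MMRM with log(post-baseline/baseline) as response and log baseline as covariate, and report ratios of geometric means. The response form is the one the SAP uses for pancreatic enzymes, and SAP 6.10.2.1 already uses a log-transformed baseline covariate for the glargine dose. Doing the same for ALT and AST is optional.

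The cost is wording and program edits on data already being collected. The downsides are that UACR results become ratios and that values below the detection limit need a stated substitution rule.
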